### **5.6.1 Numerical Rating Scale (NRS)**

The pain NRS consists of 1 question that will be asked by interviewing the subjects. The subjects will be asked to rate their average pain specific to the area(s) of chronic pain being treated over the past 24 hours on a 0 (no pain) to 10 (worst imaginable pain) scale. A higher score indicates a higher pain level. The NRS is implemented in the Baseline CRF, the End of Initial Trial Evaluation Period CRF or the End of Extended Trial Evaluation Period CRF.

### **5.6.2 Patient Reported Pain relief (PRP)**

Subjects are asked to directly estimate the percentage of pain relief experienced during the trial period from 0% (no pain relief) to 100% (total pain relief). (e.g. "I have 60% pain relief").

### **5.6.3 29-Item Adult Scale of the Patient Reported Outcomes Measurement Information System (PROMIS-29) (Deyo, Ramsay, Buckley, et al., 2016)**

The PROMIS-29 is an adult scale developed in partnership with the National Institutes of Health (NIH) to estimate overall quality of life by assessing the following domains known to impact activities of daily living: physical function, sleep disturbance, depression, anxiety, fatigue, pain interference, pain intensity, and social role satisfaction. The scale requires subjects to rate the frequency and/or severity of symptoms and experiences related to each of these domains; a numerical rating scale for pain intensity (0-10) is included on the scale. A total score is calculated and transformed against normative data into a t score indicating global quality of life in relation to population norms. Subscales are defined by each domain described above and can be examined separately to parse separate symptoms or deficiencies in quality of life. Additionally, an impact score for chronic low back pain was developed by the NIH Research Task Force (Deyo, Dworkin, Amtmann, et al., 2014), which is computed using the pain intensity, pain interference, and physical function subscales. Data captured in this scale can be used in a variety of ways to establish patient characteristics and track changes over time.

### **5.6.4 Pain Catastrophizing Scale (PCS) (Sullivan, Bishop, & Pivik, 1995)**

The PCS is a validated scale that measures the magnitude of catastrophizing (negative thoughts and feelings while a patient is experiencing pain). Subjects answer questions about how they feel and what they think about when they are in pain (i.e., not at the current moment). The scale includes 13 statements concerning pain experiences that are rated on a scale between 0 'not at all' and 4 'always'. The scale is self-administered, takes 5 minutes to complete and examines the following three domains: Rumination, Magnification and Helplessness. A higher score indicates a higher level of catastrophizing. The PCS is implemented in the Baseline CRF.

### **5.6.5 Stimulation Assessment**

The Stimulation Assessment Form includes questions to identify the sensations experienced when stimulation is used. Subjects identify the intensity and areas of sensations, if experienced. Intensity is rated on a scale of 0 (no feeling) to 10 (very intense). A map of the body is labeled with different numbered quadrants to identify the areas of sensations. The subject will be requested via interview technique to indicate the area he/she is feeling sensations. The form will be implemented at Trial System Implant (Initial Trial Evaluation) Visit CRF, End of Initial Trial Evaluation Visit CRF and End of Extended Trial Visit CRF.

## **5.7 Clinician Assessments**

The clinician assessment of the two lead implant techniques will be performed at the end of each trial implant procedure and again at the end of the study.

At the end of each trial implant procedure, clinicians will be asked to rate the magnitude of anesthesia-related difficulty experienced during the procedure, the magnitude of difficulty in placing the leads, and their affinity (liking) for the trial implant procedure performed compared to their usual practice.

Anesthesia-related difficulty and Lead Placement difficulty will be assessed with a 5-item Likert scales (No Difficulty, Little Difficulty, Moderate Difficulty, Severe Difficulty, Extreme Difficulty – could not place leads). To assess affinity (liking), clinicians will be asked: “On a scale from 0 to 4, with 0 being ‘not at all’ and 4 being ‘very much’, how much did you like this trial implant procedure compared to your usual clinical practice.” Scores will be treated as magnitude of “liking” for each procedure and will be tabulated as interval data.

At the end of the study, clinician’s comparative preference for one procedure over the other will be assessed; this will serve as the secondary endpoint. Clinicians will be asked to choose either “Anatomic Lead Placement” or “Targeted Lead Placement” in response to the following question: “Considering your subjects’ experiences and outcomes and your experiences with both lead placement techniques, which technique do you prefer?”

## **5.8 Description of Activities Performed by Sponsor Representatives**

Trained Sponsor personnel will provide technical expertise and technical guidance on the use of the SCS device, including training and proctored case coverage.

While Sponsor representatives may perform these activities, the Principal Investigator remains responsible for ensuring all clinical investigation data is collected as required per CIP.

## **5.9 Subject Study Completion**

When the subject’s participation in the clinical investigation has been completed, the subject will return to the medical care as per physician’s recommendation.

## **5.10 Subject Withdrawal**

Subjects must be informed about their right to withdraw from the clinical investigation at any time and for any reason without sanction, penalty or loss of benefits to which the subject is otherwise entitled. Withdrawal from the clinical investigation will not jeopardize their future medical care or relationship with the investigator. Subjects will be requested to specify the reason for the request to withdraw. The investigator must make all reasonable efforts to retain the subject in the clinical investigation until completion of the clinical investigation.

Examples of reasons for subject’s withdrawal include, but are not limited to:

- Subject and/or family request to withdraw consent
- Subject death
- Unsuccessful trial implant resulting in ineffective stimulation
- Lead revision
- System explant

The status of the subject’s condition should be documented at the time of withdrawal.

## **5.11 Study Committees**

### **5.11.1 Steering Committee (SC)**

A Steering Committee will advise the Sponsor on key aspects related to the development, execution, analysis and reporting, and overall conduct of the clinical investigation. A Steering Committee charter will define membership of the committee and outline the purpose, roles, responsibilities, and general rules of operation for the Steering Committee. This charter is maintained by the Sponsor and sets forth the procedures for the implementation of the Steering Committee.

A Medical Monitor will be utilized for this study. The Medical Monitor is responsible for reviewing each subject's lead placement imaging to determine if the lead placement guidelines were followed. Once the investigator completes the trial implant procedure, the images and applicable source documentation will be provided to the Medical Monitor for evaluation. If the Medical Monitor determines that the patient was implanted outside the required guidelines, a protocol deviation will be issued and the patient will be excluded from the primary endpoint analysis.

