#### 5.4.2 Randomization and Blinding

Randomization may occur at the end of the baseline visit or just prior to surgery for trial system implant (Initial Trial Evaluation Period Start) Visit.

Subjects will be randomized (1:1) using random permuted blocks of varying length and stratified by site. Subjects will be blinded to treatment group and treated in two groups as follows:

1. Group 1 (AB): anatomic lead placement followed by BurstDR™ stimulation during initial trial evaluation period
2. Group 2 (TB): targeted lead placement followed by BurstDR™ stimulation during initial trial evaluation period

Randomization assignment will be communicated to the site via the Randomization Application available in the EDC Site Portal.

Regardless of sedation, subjects will not be able to distinguish what implant technique (anatomic or targeted) is utilized without intimate knowledge of SCS programming, and with standardizing subject

interactions, the subjects will remain blinded to the treatment group. Implanting physicians and surgical support staff must follow the specific guidelines for the lead placement techniques and therefore cannot be blinded, but will be provided with a standardized script to assist with subject interaction as a way to minimize the risk of disclosing randomization assignments. Additionally, sites will be instructed to schedule study visits to restrict study subjects from being in the clinic at the same time, which aims to minimize subject to subject communication. Prior to study exit and before being unblinded, subjects will be asked about their memory for intra-operative testing as an assessment of the blind. Intra-operative testing is the key distinguishing feature between the techniques, so assessment of memory for experience will help to establish the status of the blind for each subject.

A Blinding Plan will be maintained separately which will include a listing of all parties involved in the study to manage workflow and identification of blinded and unblinded information.

[figure not shown]

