### 6.1 Hypotheses

#### 6.1.1 Primary Endpoint Hypothesis

The primary endpoint is intended to demonstrate non-inferiority of the qualification rate at the end of the initial trial evaluation period for Group 1 (AB) compared to Group 2 (TB).

For each randomization group, the qualification rate is defined as the number of subjects who are identified as "qualified for permanent system implant" divided by total subjects who complete the initial trial evaluation period for the respective randomized group.

Qualification for permanent system implant is defined by a composite in which a subject meets all of the following conditions:

- >50% patient reported pain relief (PRP) at the end of the trial evaluation period
- Trial evaluation period lasted for a minimum of 3 days
- Physician recommends subject for permanent system implant
- Subject reports a willingness to pursue a permanent system implant
- 

Subjects are not qualified for permanent system implant if they meet both of the following:

- ≤50% PRP at the end of the trial evaluation
- Trial evaluation period lasted for a minimum of 5 days

Hypothesis:

The hypothesis is formally addressed as:

$$H_0: P_{AB} - P_{TB} \leq -15\%$$

[figure not shown]
$$H_1: P_{AB} - P_{TB} > -15\%$$

where

[figure not shown]
$P_{AB}$  = permanent system qualification rate of Group 1 (AB)

$P_{TB}$  = permanent system qualification rate of Group 2 (TB)

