#### 6.1.1.1 Analysis Methodology

#### 6.1.1.2 Sample Size Determination

#### 6.1.1.3 Analysis Populations

The analysis population includes subjects who are randomized and either qualify for a permanent system implant or do not qualify for a permanent system implant, as defined earlier.

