#### 6.1.1.5 Missing Data

A sensitivity analysis will be carried in the same manner as the primary analysis, except the subjects who were randomized, underwent the trial system implant and did not complete the initial trial period will be included in the analysis and be treated as non-qualified subjects.

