The primary marker of success during the typical SCS trial evaluation period is qualification for permanent implant. Qualification per standard of care for SCS devices includes a successful trial evaluation period defined by subject's assessment of 50% or more pain relief during the trial evaluation, physician's recommendation, and the subject's willingness to continue to the permanent system. As such, the current clinical investigation defines qualification for permanent implant as a composite endpoint based upon standard of care to be used as for the primary endpoint. Demonstration of non-inferiority will establish that the anatomic placement technique is similar to traditional, targeted techniques in terms of subject selection for permanent implant. Secondary and descriptive endpoints will provide evidence of the physician and patient experience with both types of implant procedures and with the Invisible Trial System, overall.

As the primary hypothesis will be tested prior to actual permanent implant status, the clinical investigation will end at the qualification stage without consideration of the actual permanent implant status for subjects. Qualification based on efficacy, subject self-selection, and physician discretion is sufficient to make inferences about the anatomic procedure and Invisible Trial System features.

Failure to qualify for this study is contingent upon a minimum of 5 days of stimulation. Anecdotal reports indicated that burst stimulation may take up to 5 days to impart full benefit; whereas, tonic stimulation does not historically have a wash-in period to reach full benefit. As such, failures occurring before 5 days may be a product of insufficient exposure to burst therapy, and the primary endpoint is contingent upon equitable treatment between randomization arms in all other aspects excepting procedure. Additionally, subjects who fail the burst trial and proceed to an extended trial evaluation with tonic stimulation will need to ensure that they are provided sufficient time to assess the alternate stimulation mode. At present, the wash-out period for burst, if any, has not been established but is suspected to be at least a few hours and up to 2 days. As such, subject's ending their trial evaluation before 5 days without meeting criteria for qualification for permanent implant will be considered a deviation and treated as missing data. Use of this criterion will also

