## 6.7 Success Criteria

The clinical investigation will be considered a success when the primary endpoint is met.

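### Section 5.11.1 drops off-guideline implants from the primary analysis after randomization, but 6.1.1 and 6.1.1.3 state no placement condition, and no visible analysis clearly keeps these subjects

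*Combined protocol and SAP*

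**What the plan says.** Section 5.11.1 asks a Medical Monitor to check each subject's lead-placement images against the guidelines. On timing it says: "Once the investigator completes the trial implant procedure, the images and applicable source documentation will be provided to the Medical Monitor for evaluation". For a subject found off-guideline, "a protocol deviation will be issued and the patient will be excluded from the primary endpoint analysis".

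Section 6.1.1 defines each arm's qualification rate as the number qualified "divided by total subjects who complete the initial trial evaluation period for the respective randomized group". Section 6.1.1.3 reads: "The analysis population includes subjects who are randomized and either qualify for a permanent system implant or do not qualify", with both outcomes as defined earlier in the section. Neither place mentions lead position or refers to 5.11.1.

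Section 6.1.1.5 gives one sensitivity analysis, run like the primary, in which implanted subjects who "did not complete the initial trial period will be included in the analysis and be treated as non-qualified subjects". Section 6.2 adds that subjects who stop before 5 days "without meeting criteria for qualification for permanent implant will be considered a deviation and treated as missing data". Section 6.7 states: "The clinical investigation will be considered a success when the primary endpoint is met".

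The placement guidance in 5.4.3 differs by arm. Anatomic placement (AB) has fixed vertebral tip levels checked by fluoroscopy. In targeted placement (TB) the level follows the pain coverage that the patient needs.

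**The concern.** A subject who completes the initial trial period with leads judged off-guideline is out of the primary analysis under 5.11.1 and in it under 6.1.1 and 6.1.1.3. With success resting on this endpoint alone, and the secondary test in 6.3 conditional on it, the passage the analyst follows could change the trial's conclusion.

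The exclusion also depends on how the assigned technique was carried out, and technique is what the trial compares. If it removes different shares of the two arms, and the removed subjects differ in outcome, the groups compared are no longer those created by randomization. No visible analysis clearly keeps these subjects, so a reader of the results could not see what the exclusion did.

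**Working it through.** **1. The passages side by side, for a completer ruled off-guideline**

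| Section | Treatment of this subject |
|---|---|
| 5.11.1 | Excluded from the primary analysis |
| 6.1.1 | In the denominator, as a completer in the randomized group |
| 6.1.1.3 | In the population, if classed as qualified or not qualified |
| 6.1.1.5 | Not mentioned; only implanted non-completers are added |

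**2. Timing.** Section 5.4.2 places randomization at the end of baseline or just before surgery. Section 5.11.1 sends the images after the implant. The exclusion is therefore post-randomization. Early review is likely, but no visible text sets a deadline for the ruling or says whether the Monitor is masked to the qualification result.

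**3. Inputs for an illustration.** There is no plan figure to reproduce: 6.1.1.1, 6.1.1.2 and 6.4 show headings only.

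- From the documents: margin -15 points (6.1.1) and 1:1 allocation (5.4.2).
- Assumed: Wald test, one-sided 0.025, 160 completers per arm, TB rate 65% (section 2 cites 41% to 71% or more for trial success in general), and 2% of TB flagged with no outcome gap, leaving 157.

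**4. Formulas.** Let e be the share of AB flagged and g the on-guideline AB rate minus the flagged AB rate. The as-randomized rate is p = p_in - e × g, so exclusion raises the AB rate to p_in = p + e × g. With 2% to 20% flagged and gaps of 10 to 20 points, the shift is 0.02 × 10 = 0.2 up to 0.20 × 20 = 4.0 points, in either direction, against a 15-point margin.

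P(non-inferiority) = Φ((p_in - p_TB + 0.15)/SE - 1.96), where SE² = p_in(1 - p_in)/n_AB + p_TB(1 - p_TB)/n_TB.

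**5. False non-inferiority under the exclusion.** The true as-randomized difference is set at the margin: AB 50%, TB 65%.

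| AB flagged | n_AB | Gap g | p_in | P(non-inferiority) |
|---|---|---|---|---|
| 10% | 144 | +20 points | 0.52 | 5.4% |
| 10% | 144 | 0 | 0.50 | 2.5% |
| 10% | 144 | -20 points | 0.48 | 1.0% |
| 2% | 157 | +10 points | 0.502 | 2.7% |
| 5% | 152 | +10 points | 0.505 | 3.1% |

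First row: SE = √(0.52 × 0.48/144 + 0.65 × 0.35/157) = 0.0564; 0.02/0.0564 = 0.355; Φ(0.355 - 1.96) = 0.054. If both arms have 10% flagged with the same 20-point gap, the shifts cancel and the rate is 2.5%.

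**6. What keeping flagged subjects can cost** (160 per arm kept; 144 and 157 when excluded)

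- Dilution: on-guideline AB 50%, flagged AB 65%, 10% flagged. The as-randomized AB rate is 0.50 + 0.10 × 0.15 = 0.515, SE = 0.0546, and Φ(0.015/0.0546 - 1.96) = 4.6% false success, if the on-guideline difference is the target. Excluding them gives 2.5%.
- Power: on-guideline AB 65%, TB 65%, 10% flagged with a 20-point deficit. Kept, the AB rate is 0.65 - 0.10 × 0.20 = 0.63, SE = 0.0537, and power is Φ(0.13/0.0537 - 1.96) = 67.8%. Excluded, SE = 0.0550 and power is Φ(0.15/0.0550 - 1.96) = 77.8%.

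**7. A constructed data set.** AB 66/100 against TB 70/100 has a lower 97.5% bound of -16.9 points and fails. Removing 8 AB subjects, 2 of them qualified, leaves 64/92 against 70/100 and a bound of -13.4 points, which passes. It was chosen to show that the two rules can disagree, and does not show how often they would.

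**The case against.** The strongest reply is that this is a missing cross-reference. Section 6.1.1.3 does not say that all such subjects are included, so 5.11.1 can be read as a specific filter on a general definition. That reading is possible, and a reader who infers a flat contradiction goes further than the text allows. But nothing visible states the filter, and the denominator in 6.1.1 counts total completers.

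Second, a reconciling sentence may exist. Section 6.1.1.1 and the Imaging Guidelines appendix show no text, and on masking, "A Blinding Plan will be maintained separately which will include a listing of all parties involved in the study". This stands, and it limits confidence. It also rules out inferring that the Monitor will know outcomes. Even so, the printed 5.11.1, 6.1.1 and 6.1.1.3 would still need to agree.

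Third, in a non-inferiority trial a placement-adherent primary set is defensible, because keeping subjects who did not receive the intended technique can hide a real difference. This also stands: 4.6% false success by dilution is close to the 5.4% found for exclusion under the opposite assumption. The documents do not show that one set is right and the other wrong.

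Fourth, off-guideline implants may be rare. Fluoroscopic confirmation with repositioning (5.4.3) and investigator training (7.2) point that way, and the Monitor also receives source documentation, so targeted implants can be flagged too. This is fair, and is why the 2% to 5% cases are shown. A reader might infer that the exclusion favors anatomic placement. The documents give neither flagged shares nor outcome gaps, and the table runs in both directions.

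**Conclusion.** The concern holds in a limited form. As printed, the primary analysis set for the sole success criterion is not the same in 5.11.1 as in 6.1.1 and 6.1.1.3. No visible analysis clearly retains completers excluded for how the assigned technique was carried out. Because the guidelines differ by arm, unequal exclusion is plausible, though not shown.

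The size is unknown. Under the stated assumptions, false non-inferiority ranges from 1.0% to 5.4% around a nominal 2.5% when 10% of the anatomic arm is flagged with a gap of up to 20 points either way. It is 2.7% to 3.1% when 2% to 5% is flagged with a 10-point deficit. The sample size, alpha, test, flagged shares and gaps are all assumed. Confidence is medium, because the methodology text and the Blinding Plan cannot be seen.

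**What to change.** 1. Align 5.11.1, 6.1.1 and 6.1.1.3 so that they name one primary population. The default should be the one 6.1.1 already states: completers in their randomized group, with off-guideline subjects kept and the deviation recorded. If the sponsor prefers the placement-adherent set, 6.1.1 and 6.1.1.3 should say so. If 6.1.1.1 already covers this, bring it into line. The under-5-days missing-data rule in 6.2 can stay as it is.
2. Prespecify the other set as a supporting analysis at the same -15% margin, report both, and discuss any disagreement. Success under 6.7 stays with the single primary analysis.
3. Require the Monitor's ruling to be dated and recorded before, and without knowledge of, the qualification result.
4. Report by arm the number ruled off-guideline, the reasons, and their qualification rate.

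The direct cost is edits to three short sections, one extra analysis and a dated ruling form. The default also carries a statistical cost. In the working's 10% examples, keeping flagged subjects gives 4.6% false success by dilution if they do better, and lowers power from 77.8% to 67.8% if they do worse. Neither choice of primary set is free of risk, which is why both should be reported.
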